3.3 Sample size justification

We anticipate a sufficient number of patients; full time therapists are budgeted to work with six patients daily while half time therapists are budgeted to work with three patients daily.

The effect size obtained from the pilot study was 0.56 (Cohen's *d*). Based on the G*Power 3.1.9.6 program we would need to study 104 patients (52 per group) to adequately power the study assuming an alpha level of .05, power = .80, two-tailed test, and 1:1 allocation. We anticipate 20% attrition rate leading to a total of 126 patient participants.

4.0 Recruitment and Screening Methods:

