4.3 Recruitment and screening of inpatients with SCI

A convenience sample of patients with SCI will be recruited based on new admissions to inpatient rehabilitation and the participation of their rehabilitation therapist in the study. The research team will approach patients assigned to one of the enrolled therapists at the time of their admission to an SRAlab inpatient SCI unit (on floor 21 or 22).

A research assistant will screen patients newly admitted to the 21 or 22 floor for presence of a traumatic or non-traumatic SCI via admission records in Cerner. Patients must be 18 years or older at time of admission and must speak English without a translator. Potential participants must also agree to having audio recordings of their therapy sessions.

The research team will communicate with the enrolled therapist to schedule a time before, during, or after rehabilitation sessions to recruit and screen patients. We will approach eligible patients using the recruitment script and flyer after assessing initial eligibility through medical records.

Interested patients will review the informed consent document with a member of the research team.

During the consent process, patients must agree to audio recordings of their therapy sessions—they will be informed that the audio recordings focus on the therapist and not the patient, but both sides of the conversation are needed to provide context to the therapist’s verbiage. We will instruct therapists to avoid using patients’ full names when recording therapy sessions. Audio recordings will be uploaded to Shirley Ryan AbilityLab OneDrive with limited permissions to maintain privacy of therapists and patients.

5.0 Research Locations:

This protocol describes research activities that will take place at Shirley Ryan AbilityLab under review of the Northwestern IRB. Therapy sessions will be held and recorded in the usual SCI rehabilitation units on the 21 or 22 floor. Research documents will be saved on the secure SRAlab network using SRAlab-approved devices. The research team will use REDCap to collect survey data and otherwise store participant information in password-protected files on the SRAlab server.

An identical protocol will be conducted at Baylor Scott White in Texas which will be reviewed under their local IRB. Any information that the SRAlab research team must share with the Baylor research team will be stripped of direct patient identifiers, such as full name and address.

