8.3 Recruit participants – Inpatients with SCI

- Once the MI trained PTs and OTs achieve basic MI competency, the experimental phase of the study will begin. The research assistants at both sites will approach a convenience sample of eligible inpatients that the PTs and OTs in the study are treating, for participation in the study. The research assistants will recruit and consent 10-11 inpatients for each of the therapists who were trained in MI as well as for each of the therapists who were not trained in MI for a total of 126 inpatients.

- The research assistants will ask the therapists when they feel comfortable to add another patient participant to their research caseload so as not to overburden the therapist with the research tasks. The patients will be kept blinded to whether their therapist has been trained in MI or not.

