8.4 Data collection

- Patient participants will be asked demographic questions following informed consent, and the research assistant will enter answers via REDCap (see 'DemographicSurvey' under 'supporting documents). The research assistant will abstract available variables about patient demographics and SCI injury characteristics, such as diagnosis and injury level, from the medical record. The patient participant may fill out the demographic survey via REDCap themselves if they prefer – the research assistant will review the answers, confirm with medical records if available, and follow up with participants in-person to clarify as needed.
- A research assistant will complete the Pittsburgh Rehabilitation Participation Scale (PRPS) for each patient participant during one randomly selected therapy session each week throughout the 4 weeks the participant is enrolled in the study. These PRPS scores will be recorded through REDCap, averaged, and analyzed.
- A research assistant will extract demographic data for each patient from the electronic medical record as well as minutes of therapy for each day from the electronic medical record for each patient participant. Demographic data extracted from the medical records will include: age, sex, injury level and severity, traumatic vs non-traumatic, injury etiology, years of education, and marital status, at the start of participation.
- All therapists will audio record therapy sessions with their patients as many times a week as possible (at least 3 sessions). They will download the recordings to a secure site so that a weekly session can be randomly chosen to send for **Motivational Interviewing Treatment Integrity (MITI)** coding. The MITI provides a global rating on five concepts of motivational interviewing: evocation, collaboration, autonomy/support, direction, and empathy. The ratings are on a 5-point Likert scale from 1 (low) to 5 (high). An average rating of 3.5 in the five concepts is considered beginning proficiency. In addition, frequency counts of MI behaviors that are open-ended questions, simple and complex reflections and MI adherent behaviors are tallied. Summary scores of reflection to question ratio, percent open questions, percent complex reflections and percent MI adherent behavior are computed.

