[name], with research staff in the Center for Rehabilitation Outcomes Research, previously led a pilot randomized controlled trial of MI training for PTs and OTs to improve patient participation during SCI rehabilitation. The study was a single site randomized controlled study in which seven therapists were randomized to a MI training condition and seven were randomized to a no training control condition. After PTs and OTs were trained, the study enrolled and followed 62 patients undergoing inpatient rehabilitation for SCI/D. The main outcome of the study was independently rated patient participation in therapy sessions using the PRPS. The results of the study were promising. Analyses revealed a significant group effect (patients treated by MI trained therapists scored significantly higher on the PRPS ($M = 4.26$, $SD = 0.91$) compared to controls ($M = 3.79$, $SD = 1.15$) after controlling for sex, age, and trauma type. The Cohen's d was 0.56, which is a medium effect. Analyses also showed a group x time effect based on adjusted and unadjusted models (adjusted odds ratio = 0.35, $p < .01$). MI training had a larger effect relative to controls during the first 1-2 weeks while

PRPS scores converged by week 4. There was a significant time effect with PRPS scores improving over time, particularly in the control group (adjusted odds ratio = 2.36, $p < .01$).

Motivational interviewing is an evidence-based approach to behavior change counseling demonstrated to be effective in multiple meta-analyses. [name] is an expert in motivational interviewing and has used it successfully in previous physical activity and behavior change trials. [name] is an experienced trainer and a member of the international MI Network of Trainers (MINT). [name], also an experienced trainer and member of the MINT, will assist her with the training. Fidelity to the treatment protocol will be assured through education, specific training in protocol related procedures and practicing and troubleshooting the procedures in role-plays with staff in the intervention group. During the trial, [name] will assure fidelity through completion of session content and via review of audiotaped sessions for MI skill.

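### Sections 2.2, 4.3 and 8.3 conflict on when patients enter and none caps the time from admission to the first PRPS, so late entry could dilute, and unequal entry bias, the Aim 1 comparison

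*Protocol*

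**What the plan says.** Protocol section 8.4 sets the outcome clock. A research assistant rates the PRPS "during one randomly selected therapy session each week throughout the 4 weeks the participant is enrolled in the study", and the scores are averaged for analysis. The weeks are weeks of enrolment, not weeks of the rehabilitation stay.

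Three sections describe how a patient comes to be enrolled:

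- Section 2.2: patients are picked at random from the caseloads of participating therapists.
- Section 4.3: the sample is built from new admissions, and patients are approached "at the time of their admission to an SRAlab inpatient SCI unit".
- Section 8.3: eligible inpatients whom the study therapists are treating are approached, and "The research assistants will ask the therapists when they feel comfortable to add another patient participant to their research caseload".

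None of these, and no eligibility criterion, sets a maximum time from admission to consent or to the first PRPS. Section 10.1 states that therapists cannot be blinded to their group.

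On the pilot, section 1.3 reports that participation generally improved from week 1 to week 4, with a flatter slope of improvement under MI. Section 21.0 adds that "MI training had a larger effect relative to controls during the first 1-2 weeks while" scores in the two groups came together by week 4, and that the rise over time was seen particularly in controls.

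**The concern.** On the sponsor's own pilot data, both the level of the PRPS and the difference between arms depend on time. The plan fixes the four-week window relative to enrolment but leaves open how far into the stay enrolment falls.

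Two consequences follow. If patients in both arms enter some way into their stay, the averaged score gives less weight to the period in which the pilot saw the larger difference, and Aim 1 could miss a real early effect. If entry is later in one arm than in the other, the arms are compared at different points on a rising curve. Section 8.3 makes the second possible, because therapists who know their allocation influence when patients are added.

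An existing pool of mid-stay patients is realistic. Section 3.3 budgets a full-time therapist for six patients daily, so each therapist will already have a caseload when the experimental phase opens. Sections 2.2 and 8.3 do not bar those patients.

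**Working it through.** **Entry rules side by side**

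| Section | Who is approached | When | Limit on time since admission |
|---|---|---|---|
| 2.2 | Random selection from caseloads | Not stated | None |
| 4.3 | New admissions | At admission | None in days |
| 8.3 | Inpatients under treatment by a study therapist | Paced by the therapist's readiness | None |

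Under 4.3, weeks of enrolment track weeks of stay closely. Under 2.2 or 8.3 as written, they need not.

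**The plan's own figure.** Section 3.3 plans on the pilot's d = 0.56, a two-sided alpha of 0.05, power of 0.80 and equal groups, and says "we would need to study 104 patients (52 per group) to adequately power the study". A two-sample t-test with these inputs needs 51.03 per group, rounded up to 52, or 104 in total. Power at 52 per group is 0.807. The figure reproduces.

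**Why the pilot odds ratios are not used for size.** Section 21.0 gives 2.36 for time and 0.35 for group by time, without a time unit. Read per week, they stand as given. Read over the three steps from week 1 to week 4, they become 2.36^(1/3) = 1.33 and 0.35^(1/3) = 0.70 per week. If 2.36 is the control slope, the MI slope is 2.36 × 0.35 = 0.83, a decline, whereas section 1.3 describes a flatter improvement. The coding cannot be recovered, so multiplying these ratios week by week is unsafe.

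**Illustration of dilution.** Assumptions, none of them from the protocol:

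- The effects e1 to e4 in weeks 1 to 4 of the stay average 0.56 and are zero after week 4.
- Pilot week 1 means the first week of the stay.
- The standard deviation of the averaged score does not change with entry time.
- Delay is equal in both arms.
- Patients are independent, as in the section 3.3 calculation.

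If a share p of patients enters k weeks late:

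d = (1 − p) × 0.56 + p × (sum of e from week k+1 to week 4) / 4

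Example, linear decline to zero, half the patients one week late: the late patients have (0.75 + 0.37 + 0 + 0)/4 = 0.28, so d = 0.5 × 0.56 + 0.5 × 0.28 = 0.42. Power at 52 per group is 0.56, and 90 per group would be needed for 0.80.

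Cells show d / power at 52 per group:

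| Assumed e1–e4 | 25% one week late | 50% one week late | 50% two weeks late |
|---|---|---|---|
| 1.12, 0.75, 0.37, 0 | 0.49 / 0.70 | 0.42 / 0.56 | 0.33 / 0.38 |
| 1.12, 1.12, 0, 0 | 0.49 / 0.70 | 0.42 / 0.56 | 0.28 / 0.29 |
| 0.75, 0.75, 0.75, 0 | 0.51 / 0.74 | 0.47 / 0.65 | 0.37 / 0.47 |
| 0.90, 0.67, 0.45, 0.22 | 0.50 / 0.72 | 0.45 / 0.62 | 0.36 / 0.45 |

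The numbers per group needed for power 0.80 are 61–67, 74–90 and 114–202 in the three columns. With no delay, d stays at 0.56 and power at 0.81.

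**Direction of bias.** Later entry among controls places their ratings higher on the steeper curve, which hides an MI benefit. Later entry in the MI arm moves along a flatter curve, so the shift should be smaller. The protocol gives no entry times by arm, so neither shift can be sized.

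**The case against.** The strongest reply is that section 4.3 already settles entry. It speaks of new admissions, approach at admission and screening of newly admitted patients. On this view, section 8.3 only paces recruitment: when a therapist is ready, the next new admission fills the slot. A patient who is being treated may also have arrived the day before. This reading is fair, and nothing in the protocol plans for late entry. It does not remove the conflict, because 2.2 and 8.3 do not restrict entry to new admissions, and even 4.3 does not bound the gap between approach and first rating.

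Second, the protocol does not say whether pilot week 1 was counted from admission or from enrolment. If from enrolment, 0.56 may already contain ordinary delay, and dilution relative to the planning value does not follow. This stands, and makes dilution conditional. The risk from timing that differs by arm remains.

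Third, the admission date is obtainable: admission records are used for screening, and daily therapy minutes are extracted. This also stands. The gap is that the variables listed in 8.4 do not include it. The form of any adjustment may sit in an analysis plan that is not shown, but entry rules and the dates to be collected belong in the protocol.

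A reader might also infer more than the text supports:

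- That the MI effect is confined to the first weeks. Section 21.0 says larger in weeks 1 to 2 and converged by week 4.
- That windows will open around week 3 of the stay. No section describes this.
- That slower intake by MI therapists would create a spurious benefit. The flatter MI slope in the pilot makes this the weaker route.

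**Conclusion.** The point holds as an unresolved conflict with a plausible effect on Aim 1. The protocol gives three accounts of when patients enter, caps none of them, and averages four ratings counted from enrolment, although its pilot shows an outcome and a treatment contrast that both change over those weeks. Following 2.2 or 8.3 as written could dilute the contrast, and entry timing that differs by arm could bias it.

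The size cannot be derived. The distribution of entry delay, the origin of pilot week 1 and the time unit of the odds ratios are all missing. The illustrative fall in power, from 0.81 to 0.70–0.74 with a quarter of patients one week late or to 0.56–0.65 with half, shows only that modest delay could matter if the assumptions hold. It does not forecast this trial. If 4.3 is followed strictly in both arms, little of the concern remains.

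**What to change.** - Reconcile sections 2.2 and 8.3 with the rule in 4.3: new admissions, approached at admission.
- Add one prespecified maximum interval from admission, or from the first session with the enrolled therapist, to the first PRPS, identical in both arms. Seven days would be one workable choice; the protocol offers no basis for a particular number.
- In 8.3, let therapists pause study intake, but do not let them add a patient later in the stay.
- In 8.4, record the admission date and the date of the first session with the enrolled therapist, and adjust the PRPS comparison for time since admission.

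The cost is a protocol amendment and two dates from the medical record. Some patients already under treatment could no longer be enrolled, so intake per therapist may be slightly slower.

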1.1 Purpose

We plan to conduct a multi-site randomized controlled trial of motivational interviewing (MI) training for physical therapists (PTs) and occupational therapists (OTs) who treat people with SCI during inpatient rehabilitation. We will test whether patients treated by MI trained PTs and OTs demonstrate greater participation in therapy sessions and better functional, social, and educational/occupational outcomes relative to patients treated by therapists without MI training. This stage of research is appropriate because a Neilsen Foundation funded pilot study that we recently completed had promising results. Study results showed that SCI patients treated by MI trained PTs and OTs participated significantly more actively in therapy sessions compared to controls. However, the study had several limitations that need to be addressed to produce a more definitive and influential trial. First, the study was conducted at a single site and results may not generalize to other sites. Second, we did not examine whether MI training and improved participation resulted in patients having better clinically meaningful outcomes such as higher likelihood of discharge to home or superior functional, social, or educational/occupational outcomes. Third, therapists trained in MI achieved only minimal competency in MI skills. We hypothesize that if therapists received ongoing coaching to improve their MI

skills during the trial the positive impact on patient participation and other outcomes might be even more robust.

1.2 Project Aims:

1. To determine whether inpatients with SCI/D treated by PTs and OTs who receive MI training and coaching demonstrate greater therapy participation compared to those treated by therapists who do not receive MI training and coaching.
2. To determine whether inpatients with SCI/D treated by PTs and OTs who receive MI training and coaching demonstrate greater functional improvement at discharge from inpatient rehabilitation and greater community integration at 6 months after discharge compared to those treated by therapists who do not receive MI training and coaching.
3. To document an effect of training and coaching on MI skills and explore potential moderators and mediators of the effect of the intervention on therapy participation.

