15.0 Audio/Video Recording/Photography

Therapy sessions will be audio recorded 2 times per week on mobile audio recording devices. The research team led by [name] will provide the therapist participants with the devices after they are enrolled in the study. The recordings will be the length of the therapist's typical session, approximately one hour but up to two hours. The therapists will download the audio recordings to a secure file (Shirley Ryan AbilityLabMicrosoft Teams secure network). Then [name] and [name] will listen to a sample of the audio recordings and rate the therapists' competency in MI using the Motivational Interviewing Treatment Integrity skill coding system during the baseline and MI competency phase.

Audio recordings will be stored separately from participant identifiers and will be labeled with Subject ID #'s rather than names. Audio recordings will be uploaded to Shirley Ryan AbilityLab OneDrive with limited permissions to maintain privacy of therapists and patients.

Participants will be informed of audio recordings during the informed consent process and throughout their study participation period. Audio recordings will be deleted after completion of the data analysis period.

During the randomized control trial phase, one random recording per week per patient participant will be shared with the Motivational Interviewing Treatment Integrity coding lab who will rate the motivational interviewing skills of the therapists by listening to 20 minutes of the recording and rating the session using the MITI 4.2.1 rating scale. These scores will be used to provide feedback to the therapists on their MI skills and to guide coaching sessions of the therapists for their MI skills. Coaching sessions of the therapists will take place individually approximately monthly or more often as needed based on the MITI scores.

16.0 Potential Benefits of this Research:

16.1 Therapist participants will be trained in motivational interviewing, an evidence-based skill that requires at least 16 hours of training by a designated instructor. Therapists who are not randomly assigned to the MI group during the

study period will have the opportunity to be trained in MI after completion of the study period. CEU credits will be offered upon completion of the MI workshop.

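### The weekly MITI session is drawn separately from the PRPS session and only from recordings that unblinded therapists chose to make, which could bias the Aim 3 skill contrast and adds some noise to any MITI-PRPS analysis

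*Protocol*

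**What the plan says.** Section 8.4 sets up two weekly samples per patient.

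- **Participation.** A research assistant completes the PRPS "during one randomly selected therapy session each week throughout the 4 weeks the participant is enrolled in the study". The handling is then given as "These PRPS scores will be recorded through REDCap, averaged, and analyzed".
- **MI skill.** "All therapists will audio record therapy sessions with their patients as many times a week as possible (at least 3 sessions" is the instruction for recording. The files are uploaded "so that a weekly session can be randomly chosen to send for" MITI coding. Section 15.0 confirms one random recording per patient per week, of which 20 minutes are coded.

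No sentence says that the two sessions are the same, that the PRPS session must be recorded, or which sessions a therapist should record.

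Three other places matter. Section 10.1 says therapists cannot be blinded. Section 15.0 uses the MITI scores for feedback and coaching, and section 1.2 places coaching in the MI arm. Aim 3 in section 1.2 is to document the effect of training and coaching on MI skills and to "explore potential moderators and mediators of the effect of the intervention on therapy participation".

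The weekly number of recordings is at least 3 in section 8.4, 2 per patient in sections 8.5 and 14.0, and 2 in section 15.0 ("Therapy sessions will be audio recorded 2 times per week on mobile audio recording devices").

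**The concern.** There are two separate issues.

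**Who chooses the sampling frame.** A random draw from a self-selected pool is not a random sample of therapy sessions. The person being scored decides what enters the pool, knows the allocation and, in the MI arm, knows that the score leads to coaching. If MI-arm therapists tend to record sessions in which MI goes well and control therapists do not, the skill contrast in the first half of Aim 3 is too large. Scores that flatter the therapist would also misdirect the coaching.

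**Whether skill and participation are seen together.** With two unlinked draws, most weekly MITI scores come from a different session than that week's PRPS score. Any exploratory analysis that links the two then works with a noisier skill measure and could miss a real mediator.

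Both are data-collection rules. No later analysis can pair sessions that were never both observed and recorded, or undo selection of the recordings.

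**Working it through.** The protocol gives no figure to reproduce here, so every size below rests on stated assumptions.

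**Inputs from the protocol:** one PRPS session and one MITI recording per patient per week; 4 weeks; 2 or 3 recordings a week; PRPS averaged; about 10 patients per therapist.

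**Assumed inputs:** S sessions a week from which PRPS is drawn, 3 to 10 with 5 as the main case; correlation r between MITI scores of two sessions with the same patient, 0.4 to 0.7, taken as equal within and across weeks.

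**1. Chance that the draws coincide.** If PRPS is drawn evenly from S sessions, the chance of hitting the MITI session is p = 1/S.
- S = 3: 0.33. S = 5: 0.20. S = 10: 0.10.
- At S = 5, the chance of no match in 4 weeks is 0.80^4 = 0.41.
- At S = 5, the chance that the PRPS session was recorded at all is 3/5 = 0.60 with 3 recordings and 2/5 = 0.40 with 2.

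**2. Association retained, single-session pairs.** Relative to same-session pairing, the fraction kept is p + (1 - p)r.

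| p | r = 0.4 | r = 0.7 |
|---|---|---|
| 0.10 | 0.46 | 0.73 |
| 0.20 | 0.52 | 0.76 |

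**3. Association retained, 4-week means.** This matches the averaged PRPS of section 8.4. The covariance of the two means is r + p(1 - r)/4 and the variance of each is r + (1 - r)/4, so the fraction kept is (4r + p(1 - r))/(1 + 3r).

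| p | r = 0.4 | r = 0.7 |
|---|---|---|
| 0.10 | 1.66/2.2 = 0.75 | 2.83/3.1 = 0.91 |
| 0.20 | 1.72/2.2 = 0.78 | 2.86/3.1 = 0.92 |

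**4. Therapist means.** With 10 patients × 4 weeks = 40 recordings and the same r throughout, the fraction is (40r + p(1 - r))/(1 + 39r). It runs from 16.06/16.6 = 0.97 to 28.06/28.3 = 0.99.

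**5. Room for selection of recordings.** Suppose a therapist records only the best R of S sessions. The mean MITI score is then overstated by the expected mean of the top R of S normal draws, in within-therapist SD units (simulated). At S = 5:
- R = 3: 0.55 SD. R = 2: 0.83 SD.
- If choice and skill correlate only 0.3: 0.3 × 0.55 = 0.17 SD and 0.3 × 0.83 = 0.25 SD.
- If choice is unrelated to skill: zero.

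These are shifts for one therapist. The arm contrast moves only by the difference in shift between the arms.

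**6. Recording counts side by side.** Section 8.4 (at least 3) and section 15.0 (2) state no denominator. Sections 8.5 and 14.0 say 2 per patient. If all counts are per patient, 3 and 2 conflict. If 8.4 is per therapist and the others are per patient, they agree only when the therapist has at least two enrolled patients (2 × 2 = 4, against 2 × 1 = 2).

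**The case against.** Much of the opposing case stands.

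- **Aim 3 states no session-level analysis.** A reader might infer that the trial relates skill in one session to participation in another, and so loses roughly a quarter to a half of the association (step 2). The protocol does not support that. It names neither a mediator nor a session-level model, and PRPS is averaged. Training is randomised to therapists, so average therapist skill is a natural mediator, and it hardly needs matched sessions (step 4).
- **Inflated skill is not shown.** A reader might infer that the design overstates the training effect. Both arms record, so the contrast is biased only if selection differs by arm. The request to record as often as possible and the $5 per upload favour recording more rather than picking the best. The text does not say that therapists may pick freely; it only gives no rule. Differential selection is plausible because only one arm is coached on MITI, but it remains a risk.
- **Matching has costs.** Announcing the session beforehand would tell unblinded therapists which session produces the Aim 1 measure. Section 2.2 requires only one enrolled therapist per patient, and 8.4 does not restrict PRPS to that therapist's sessions, so some PRPS sessions may have no recorder. An engaged patient may also make good MI easier, so same-session pairing can inflate the association. The first two points shape the fix. The third is a caution for interpretation.

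The objection does not remove two facts: the scored person controls the sampling frame, and the recording counts are not aligned.

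**Conclusion.** The point holds as a limited weakness in data collection for Aim 3. The two weekly draws are unlinked, and the MITI draw is random only within recordings that unblinded therapists chose to make.

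The skill contrast could be biased if selection differs by arm. At an assumed 5 sessions a week, the shift for one therapist ranges from zero to 0.55 SD (3 recordings) or 0.83 SD (2 recordings), with 0.17 to 0.25 SD under weak selection. For a link between MITI and PRPS, the loss is modest with 4-week means (about 75-92% retained) and negligible with therapist means. It is larger only at session level (46-76%). All these figures depend on assumed values of S and r; a weaker correlation across weeks would lower the retained fractions.

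Aims 1 and 2, and the sample size, are not affected.

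**What to change.** In sections 8.4 and 15.0, take the choice of coded session away from the therapist:

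1. The research team draws the week's session at random, as it already must for PRPS.
2. The recorder is switched on when the research assistant arrives to rate PRPS, with no advance notice to the therapist.
3. That recording goes for MITI coding.
4. If the PRPS session is not with an enrolled therapist, or the file fails, a back-up recording is used, from a session that the team designated at random.

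Reconcile the number of recordings a week across sections 8.4, 8.5, 14.0 and 15.0, and state whether it is per patient or per therapist.

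**Cost:** protocol wording and a routine on the unit. The numbers of PRPS visits and MITI codings do not change. The small downside is that MITI is then scored mostly in sessions with an observer present.
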